### 6.1.2 Losartan Titration Description

#### Dose Rationale

The dose ranges used for the losartan trial for a pediatric hypertension have been between 0.05 to 2.5 mg/kg/day, with higher doses improving blood pressure in these patients (70). This trial represented one of three successful anti-hypertensive drug trials out of a total six studied in Benjamin *et al.*, 2008, that evaluated the appropriate outcome endpoints and dose ranges in pediatric populations. The authors speculated that the higher doses utilized and the availability of a pediatric formulation were potentially responsible for the successful completion of those three trials as these represented features in common among the successful drug trials (76). Further, the dose used in the losartan trial for hypertension exceeds the upper planned limit of ~1.4 mg/kg in pediatric patients for the proposed EoE Losartan trial, and has previously been used in the study of losartan in patients with Marfan's Syndrome (59). In this small cohort study of Marfan's patients, the rate of change in the aortic root diameter was significantly decreased in patients treated with losartan who had previously failed other medical therapy (59). A lower dose is of further importance in this study, as there is the risk of postural orthostatic tachycardia syndrome in patients with EDS. The adult dose ranges are derived from well-established ranges described in the prescribing information available for losartan.

#### Enrollment - Initiation of Study Agent: Titration Cycle 1

For enrolled participants, approximately 0.7-0.9 mg/kg will be given on days 1-21 for enrollees less than 18 years of age and 50 mg for those 18 and older as per dosing commonly recommended for hypertension in pediatric and adult patients. These dosing instructions represent a common starting dosing for pediatric and adult patients undergoing treatment for hypertension. A daily maximum dose of 100 mg per day will be allowed for all participants regardless of age as this study is designed to minimize risks associated with hypotension in patients agreeing to enroll in this study.

Of note, in review of patients enrolled into the CCHMCEGID research database, 5% of all EoE patients have a weight which exceeds 90 kg. When limited to those EoE patients who are 18 and older, this percentage climbs to 8%. This indicates that the pool of patients is small and only a few patients would be at risk for the maximum dose planned for this clinical trial at the outset of their enrollment. Review of blood pressures for 6 subjects enrolled in the trial to date reveals that the lowest systolic and diastolic blood pressure percentiles were 27th and 21st percentile respectively following initiation of losartan.

The participants will be instructed to call the study coordinator or the study physician if any Adverse Drug Reactions (ADRs) occur. On day 6, 7, or 8, after each dosing visit, the study coordinator will contact each participant (or parent/legal guardian) and verify the absence of ADRs.

After each participant has taken the study agent for at least 21 days but less than 28 days (7-day window), they will return to the clinic for a visit. During that visit the research staff will verify the absence of ADRs. If no reported ADRs the participants will then proceed to Cycle 2 (see below).

#### Up-titration: Titration Cycle 2

Up-titration will proceed according to the schedule outlined in Table 2. The dose of study agent will be increased as tolerated to a dose of approximately ~1.4 mg/kg, not to exceed 100 mg. The maximum dose will continue through the maintenance phase. For each cycle, after participants have taken the agent for at least 21 days but less than 28 days (7-day window), the study coordinator will verify the absence of ADRs.

6.1.3 Table 2: Losartan titration schedule

Duration of Dosing for each Titration Cycle	Initiation	Up-Titration	Down-titration Increment
	Titration Cycle 1	Titration Cycle 2	(See Section 6.4)
21-28 days	0.7-0.9 mg/kg	1 - 1.4 mg/kg (maximum 100 mg)	1 st : twice-a-day dosing* 2 nd : 0.2 mg/kg/d

\*e.g. For a dose of 50 mg once a day associated with significant hypotension, the patient would first be down-titrated to 25 mg twice a day. If this were insufficient to control symptoms, the dose would be reduced by 0.2 mg/kg/d until the subject is asymptomatic.

#### 6.1.4 Administration and Preparation of Losartan

Losartan tablets (25 and 50 mg) will be used for patients not requiring a suspension. Bottles of ten 50 mg tablets that will be used to prepared suspension form (200 ml for 2.5 mg/mL) at the site pharmacies will be used in this trial.

##### Preparation of Suspension

Preparation of suspension will follow the directions located in the Product Insert (Sections 5.1-5.2) and in the Pharmacy Manual. Each bottle sent to the site will contain ten 50 mg tablets. Once prepared at the site pharmacy the suspension will be stored at 2 to 8 degrees Celsius and must be discarded after 4 weeks from date of preparation.

## 2. Drug Accountability

Under Title 21 of the Code of Federal Regulations (21CFR§312.62), the investigator will maintain adequate records of the disposition of the investigational agent, including the date and quantity of the drug received, to whom the drug was dispensed (participant-by-participant accounting), and a detailed accounting of any drug accidentally or deliberately destroyed.

Records for receipt, storage, use, and disposition will be maintained by the study site. A drug-dispensing log will be kept current for each participant. This log will contain the identification of each participant and the date and quantity of drug dispensed.

All records regarding the disposition of the investigational product will be available for inspection.

Study agent will be dispensed through the site Investigational Drug Service per its standard operating procedures (SOPs). All study agent administered to each participant will be recorded on the Drug Accountability Form maintained by the Investigational Pharmacy.

*Tablet/Suspension Dispensing:* The participant (or parent/legal guardian) will receive a medication. Participant specifies study agent in the form of tablets or suspension will be dispensed by the pharmacy every 3 to 4 weeks. Unused study medication will be returned and retained until study completion.

At the end of the study, the study monitor will be responsible for study agent reconciliation. All unused study agent will only be disposed and discarded after authorization from NIAID per guidelines outline in the Pharmacy Manual. All study documents located in the Investigational Pharmacy should be moved to the investigator binder at the end of the study to ensure that all study documentation is maintained in one location.

## 3. Assessment of Participant Compliance with Investigational Agent

The study coordinator will perform medication accountability and calculate the level of compliance.

## 4. Toxicity Prevention and Management

If a participant develops certain ADRs such as fatigue or dizziness, the study agent can be changed to night-time administration or twice-a-day administration at the discretion of the PI. If drug reactions persist or abnormalities are noted in the safety lab work, the dose of the study agent will be decreased by the down-titration increments listed in Table 2. The participant will be withdrawn from the study if serum creatinine, serum potassium, AST, or ALT are increased such that they would be classified as a moderate or more severe AE according to the schema in the Common Terminology Criteria for AEs (CTCAE) (77). For serum creatinine, this value is greater than 1.5 times the upper limits of the age-matched normal value; for potassium, this value is 5.6-6.0 mEq/L in a non-hemolyzed sample; and for AST and ALT, this value is greater than 2.5 times the upper limit of the age-matched normal value. Abnormal laboratory values for serum creatinine, serum potassium, AST, and ALT will always be measured twice to re-examine for error.

If the participant's blood pressure (systolic and diastolic) falls below the 2nd percentile for age listed in the study staff-generated guideline report for blood pressure ranges for children and adolescents (See section 19) and has concurrent symptoms of hypotension, the participant's dosage will be decreased by the down-titration increments listed in Table 2. If the participant is asymptomatic, this will not be considered hypotension. Participants will be re-evaluated after down-titration of the study agent at the PI's discretion. Unlike the situation with heart-rhythm abnormalities associated with withdrawal of beta-blockers (78), there is no similar literature noted for ARB medications and no taper of losartan is planned following completion of the study.

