#### Exclusion Criteria

Individuals who meet any of these criteria are not eligible for enrollment as study participants:

1. Any past or planned cardiac surgery.
2. An aortic root Z-score  $\geq 3.0$  on a previous echocardiogram.
3. Intolerance to the study agent (i.e., losartan) such as angioedema, immunoglobulin E (IgE)-mediated allergy, etc.
4. A mean blood pressure measurement (both systolic and diastolic) at screening that is below the 2nd percentile for his/her age as listed in the study staff-generated guideline report for blood pressure ranges for children and adolescents (See section 19), and is currently experiencing hypotension symptoms (1). If the participant is asymptomatic, this will not be considered hypotension.
5. Renal dysfunction with creatinine in excess of the upper normal limit for age
6. Another disorder that causes esophageal eosinophilia (e.g., hypereosinophilic syndrome, Churg-Strauss vasculitis, eosinophilic granuloma, or a parasitic infection).
7. A diagnosis of hepatic insufficiency (e.g. liver failure, history of liver transplantation, or persistent liver transaminase elevation).
8. A history of abnormal gastric or duodenal biopsy or documented gastrointestinal disorders (e.g., Celiac Disease, Crohn's disease or *Helicobacter pylori* infection), not including chronic gastritis, chronic duodenitis, mucosal eosinophilia or other eosinophilic gastrointestinal disorders (EGIDs).
9. Use of anti-IgE monoclonal antibody (mAb), anti-tumor necrosis factor [TNF] mAb, anti-IL-5 agents, or anti-IL-13 within 6 months prior to study entry (i.e., screening).
10. Use of methotrexate, cyclosporine, interferon  $\alpha$ , or other systemic immunosuppressive or immunomodulating agents within 3 months prior to the screening visit.
11. A stricture during endoscopy procedure that prevents passage of the endoscope

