### 3. Exclusion Criteria

Individuals who meet any of these criteria are not eligible for enrollment as study participants :

1. Any past or planned cardiac surgery.
2. An aortic root Z-score  $\geq 3.0$  on a previous echocardiogram.
3. Intolerance to the study agent (i.e., losartan) such as angioedema, immunoglobulin E (IgE)-mediated allergy, etc.
4. A mean blood pressure measurement (both systolic and diastolic) at screening that is below the 2nd percentile for pediatric participants and below the 5th percentile for adult participants as listed in the study staff-generated guideline report for blood pressure ranges for children and adolescents (Refer to Manual of Operations (MOO)),
5. Renal dysfunction with creatinine in excess of the upper normal limit for age.
6. Another disorder that causes esophageal eosinophilia (e.g., hypereosinophilic syndrome, Churg Strauss vasculitis, eosinophilic granuloma, or a parasitic infection).
7. A diagnosis of hepatic insufficiency (e.g. liver failure, history of liver transplantation, or persistent liver transaminase elevation).
8. A history of abnormal gastric or duodenal biopsy or documented gastrointestinal disorders (e.g., Celiac Disease, Crohn's disease or *Helicobacter pylori* infection), not including chronic gastritis, chronic duodenitis, mucosal eosinophilia or other eosinophilic gastrointestinal disorders (EGIDs).
9. Use of anti-IgE mAb, anti-TNF mAb, anti-IL-5 agents, or anti-IL-13 within 6 months prior to study entry (i.e., screening).
10. Use of methotrexate, cyclosporine, interferon  $\alpha$ , or other systemic immunosuppressive or immunomodulating agents within 3 months prior to the screening visit.
11. A stricture during endoscopy procedure that prevents passage of the endoscope.
12. Taking or is planning to take an ARB, ACEI, BB, or calcium-channel blocker therapy at the screening visit or at any time during the study or has been taking any of these medications for 3 months prior to the screening visit.
13. Taking or is planning to take hydrochlorothiazide, digoxin, warfarin, cimetidine, phenobarbital, rifampin, or fluconazole.

14. Is taking or is planning to take potassium supplements or salt substitutes containing potassium.

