## 5.2 Risks of Investigational Product or Intervention cited in Medical Literature

### Postmarketing Experience

The following additional adverse reactions have been reported in postmarketing experience:

*Digestive:* Hepatitis (reported rarely).

*General Disorders and Administration Site Conditions:* Malaise.

*Hematologic:* Thrombocytopenia (reported rarely).

*Hypersensitivity:* Angioedema, including swelling of the larynx and glottis, causing airway obstruction and/or swelling of the face, lips, pharynx, and/or tongue has been reported rarely in patients treated with losartan; some of these patients previously experienced angioedema with other drugs including ACE-inhibitors. Vasculitis, including Henoch-Schönlein purpura, has been reported.

Anaphylactic reactions have been reported.

*Metabolic and Nutrition:* Hyperkalemia, hyponatremia have been reported with losartan.

*Musculoskeletal:* Rare cases of rhabdomyolysis have been reported in patients receiving angiotensin II receptor blockers.

*Nervous system disorders:* Dysgeusia.

*Respiratory:* Dry cough (see above).

*Skin:* Erythroderma.

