### 3. Reducing Risks of Losartan Use

To minimize the potential risks of losartan, the starting doses of the study agent will be relatively low and will be up-titrated carefully (See section [6.1.2](#)). Participants will be followed closely for adverse drug reactions (ADRs) and will only be up-titrated if the current study agent dose is tolerated. In addition, clinical labs (i.e., complete blood count [CBC] with differential and chemistry) will be measured to monitor serum creatinine, potassium, hemoglobin, hematocrit, AST, and ALT; any abnormalities in laboratory values that are determined to be AEs will be evaluated and managed by the Investigator.

Pregnancy or planned pregnancy during the trial is exclusionary as losartan exposure represents a high-risk problem for the fetus if a mother is inadvertently exposed to losartan during pregnancy. The use of losartan would not merit potential benefit in EoE, given the significant risk of frank mortality and morbidity to the fetus associated with these exposures. At the time of informed consent and throughout the study, female participants of childbearing potential and their legal guardians will be educated and notified about the potential risk of the study agent. The risk will also be described in the consent and the assent forms. Birth control measures will be required for female participants of childbearing potential.

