## 8.2 Visit 2 Enrollment / Titration Cycle 1 / (Week 0)

All eligible participants will be enrolled into the study at Week 0 if they meet all eligibility criteria and have completed the screening procedures. Screening and enrollment visits may be combined when deemed necessary. If the screening and enrollment visit are combined, the study drug will not be dispensed until all inclusion and exclusion criteria have been met and all screening visit procedures have been performed. This includes the review of all laboratory tests performed during the screening portion of the visit. If a participant is screened and enrolled within a 5-day time frame, study procedures that would be repeated will only be performed once. The enrollment visit also marks the beginning of the Treatment Phase and Titration Cycle 1. At this visit, staff members will:

- Reassess eligibility (inclusion and exclusion criteria)
- Conduct vitals (blood pressure, heart rate, respiratory rate, temperature), height, and weight
- Administer patient- and parent-reported outcome questionnaires
- Urine pregnancy test in females of childbearing potential
- Assess and inquire about AEs
- Assess concomitant medications and/or therapies
- Assess participant compliance with diet
- Dispense study agent with instructions

- Dispense diet and medication log

The PI or the sub-investigator will determine the initial dose of study agent per the titration schedule in Sections [6.1.2 - 0](#). The participant's weight obtained at this visit will be used to calculate the initial dose of losartan. The Investigational Pharmacy will dispense the appropriate dose and amount of the study agent per the Manual of Operations (MOO). The participant will be instructed to administer the study agent orally once daily, at approximately the same time each day, with or without food, for at least 21 days but less than 28 days. The participant will also be instructed to record the start and stop date of the study agent and each dose in the study diary. The participants will be instructed to call the PI and/or study coordinator if they have any questions, concerns, adverse events, or changes in medication.

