#### Lab Results

- Any result that is listed as clinically significant by the site or protocol PI, the independent medical monitor and/or the NIAID Medical Monitor.

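### The entry criteria set no serum potassium limit, so a candidate already at the 5.6 mEq/L withdrawal level can be enrolled and dosed for 21 to under 28 days before the next scheduled chemistry

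*Protocol*

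**What the plan says.** Section 6.4 (Toxicity Prevention and Management) requires withdrawal when creatinine, potassium, AST or ALT reaches moderate grade or worse. For potassium the level is given as a range: "for potassium, this value is 5.6-6.0 mEq/L in a non-hemolyzed sample". Because worse grades also count, the working threshold is its lower end, 5.6 mEq/L. The same section requires abnormal values of these four tests to be measured twice.

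The entry criteria treat these tests differently. Exclusion 5 sets a creatinine limit: "Renal dysfunction with creatinine in excess of the upper normal limit for age". Exclusion 7 covers hepatic insufficiency, with persistent transaminase elevation as an example. The only criterion that names potassium is exclusion 14: "Is taking or is planning to take potassium supplements or salt substitutes containing potassium". The synopsis has the same three criteria.

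The protocol recognizes the risk. Section 5.2 states: "Hyperkalemia, hyponatremia have been reported with losartan". Section 1.5 describes a severe case (potassium 7.6 mEq/L) in a child taking losartan with an ACE inhibitor, who had renal insufficiency, a history of borderline high potassium, and septic shock. It then says that this trial excludes renal insufficiency (exclusion 5) and common antihypertensives (exclusion 12). It does not return to baseline potassium.

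**The concern.** Creatinine must be within normal limits at entry and leads to withdrawal only at a higher level. Potassium has a withdrawal level but no entry limit. A site that applies the eligibility list as written has no criterion on which to refuse a candidate whose potassium is already at the withdrawal level, and the schedule then provides no chemistry until the participant has had three to four weeks of losartan.

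What is at stake is participant safety, in a trial that enrolls from age 5. There is also an avoidable loss: a participant still at 5.6 mEq/L or more at Visit 3 would be withdrawn under section 6.4 and replaced under section 10.3.

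**Working it through.** No sample size, power or error-rate figure is involved. The check is a reading of the criteria and the schedule against each other.

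**1. Entry criteria.** Of the 6 inclusion and 18 exclusion criteria, the number with a serum potassium limit is 0 in section 4 and 0 in the synopsis.

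**2. Entry limit against withdrawal level.**

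| Test | Entry limit | Withdrawal level (section 6.4) |
|---|---|---|
| Creatinine | 1.0 × upper normal limit (exclusion 5) | above 1.5 × upper normal limit |
| Potassium | none; intake only (exclusion 14) | 5.6 mEq/L, non-hemolyzed |
| AST, ALT | persistent elevation, no number (exclusion 7) | above 2.5 × upper normal limit |

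Creatinine has a margin of 1.5 − 1.0 = 0.5 × upper normal limit. The documents give no upper normal limit for potassium, so no corresponding margin can be calculated.

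**3. Scheduled chemistry (sections 8.1 to 8.8 and Table 4).** Chemistry is drawn at screening (Week −12 to 0), then at Weeks 4, 8, 12 and 16. Visit 2 (Week 0) and the Week 1 contact list none.

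**4. Exposure before the first on-treatment chemistry.** Section 8.4 places Visit 3 after at least 21 and fewer than 28 days on drug. Table 4, footnote b, says no more than 28 days. The general ±7-day window around Week 4 (day 28) would by itself allow 28 − 7 = 21 to 28 + 7 = 35 days. I use the specific rule in section 8.4. The dose over that time is about 0.7 to 0.9 mg/kg daily, or 50 mg at age 18 or older (section 6.1.2).

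**5. Longest interval between scheduled chemistries.** Screening may be up to 12 weeks before enrollment. The interval can then be 12 weeks + 21 days = 15 weeks, up to just under 12 weeks + 28 days = 16 weeks.

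**6. A worked case.** Take a candidate with a repeat-confirmed, non-hemolyzed screening potassium of 5.7 mEq/L, normal creatinine, no potassium supplements and no excluded drugs. No criterion excludes this person on potassium. Section 8.2 enrolls those who meet all criteria and have completed screening. Losartan starts, and potassium is next scheduled for measurement 21 to under 28 days later. If it is still 5.6 mEq/L or more, section 6.4 requires withdrawal.

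**7. Cost if that happens once.** One replacement is 1/15 = 6.7% of the planned total, or 1/5 = 20% of the EoE-CTD group. At the planned 30 screened for 15 enrolled, it needs about 30/15 = 2 further screenings. These figures apply to any single withdrawal and say nothing about how likely this one is.

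**The case against.** The strongest reply is that section 6.4 already bars such a candidate. Its withdrawal rule is not limited to on-treatment samples, adverse events are collected from consent (section 11.6.1), and section 11.4 counts grade changes between screening and baseline as adverse events. On that reading, a consented person at 5.7 mEq/L meets a withdrawal rule before the first dose. The reading is possible. But the rule sits under toxicity management, speaks of values that have increased, and is not an eligibility criterion. If it is the intended reading, writing it into section 4.3 changes nothing except the clarity.

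Second, the value would be seen. When screening and enrollment are combined, drug is withheld until the screening steps are done: "This includes the review of all laboratory tests performed during the screening portion of the visit". That review is compulsory, as is the repeat of an abnormal value, so a reader who infers that protection rests wholly on judgement goes too far. What remains discretionary is the action taken on the value. The review sentence is written for combined visits and names no potassium level that stops dispensing. Section 5.3 likewise leaves the response to the site: "any abnormalities in laboratory values that are determined to be AEs will be evaluated and managed by the Investigator". So does section 11.3.1: "Any result that is listed as clinically significant by the site or protocol PI".

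Third, the protocol addresses causes of hyperkalemia through exclusions 5, 12 and 14. This is a considered strategy and it lowers the risk. It still leaves out baseline potassium, which section 1.5 mentions alongside the two factors that it does answer.

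A reader might also infer the same gap for AST and ALT. The documents do not support a new criterion there: exclusion 7 already covers persistent transaminase elevation with no lower bound, which for persistent elevation is stricter than a cutoff at 2.5 × upper normal limit.

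**Conclusion.** The point holds for potassium alone. As the eligibility criteria are written, a candidate at or above 5.6 mEq/L can be enrolled and take losartan for 21 to under 28 days before the next scheduled chemistry. This is a worthwhile and inexpensive safety improvement, not a flaw that undermines the trial.

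It rests on two assumptions: that section 6.4 governs participants on study and not entry, and that the Manual of Operations, which is not among the documents, sets no potassium limit before dispensing.

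A reader might infer that such dosing is likely, or that the trial stands to lose 6.7% of its participants. Neither follows. The documents do not say how often screening potassium reaches 5.6 mEq/L, and a physician who saw such a value might well decline to start the drug. The method of the primary efficacy analysis is not affected.

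**What to change.** Add to section 4.3 and to the synopsis an exclusion for a repeat-confirmed, non-hemolyzed screening serum potassium of 5.6 mEq/L or more. State in section 8.2 that the screening potassium must be reviewed and below this limit before drug is dispensed, whether or not the visits are combined. Leave exclusion 7 as it is.

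The change is to protocol wording. It uses chemistry already drawn at screening, and only an abnormal value needs a repeat, as section 6.4 already requires on study. The downside is an occasional screen failure in a small trial. One limit remains: a screening sample may be up to 12 weeks old at enrollment, so the criterion shows that potassium was acceptable at screening, not on the day of the first dose.
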